Enrolled patients will fill out a brief data collection form to include age, sex, race, phone number, and baseline headache severity using a 100-mm visual analog scale (VAS). Repeat headache severity scores will be measured at 15, 30, 45, and 60 minutes. Time zero begins immediately after complete administration of the study drug. Nausea (with a 100 m VAS), vomiting, anxiety, restlessness (akathisia), heart rate, and blood pressure will also be assessed at these time intervals. The need for rescue medications will be extracted from the patient’s chart at a later time.

Trained research assistants will call the patient 24-48 hours post-discharge by phone to ask them to rate their satisfaction with the drug they received on a scale of 0-10, and to

ask if they are currently having a headache (yes or no). If the patient is admitted, the patient will be approached in the hospital by an investigator or research assistant for follow up.

Outcome Measures

The primary outcome measure will be the difference in pain scores between the prochlorperazine and ketamine groups, measured as the absolute difference between the means at 60 min. Secondly, we will measure the difference between the rates of decline in pain scores, rate of admission, nausea scores, rate of vomiting, rate of development of akathisia, rate of use of additional medications for headache, heart rate and blood pressure changes, headache resolution with telephone follow up, and patient satisfaction.

Privacy and Security

In order to protect the privacy of the research subjects and to maintain the confidentiality of data, all data will be managed only by trained research assistants or investigators and will be stored in the locked Emergency Medicine research offices and electronic data will be stored on a password protected computer in the locked Emergency Medicine research office. All research assistants and investigators are HIPAA- trained, CITI trained and credentialed by UMC IRB, and oriented to the study protocol.

Data Analysis:

A couple prior studies have used a 25-mm difference in mean VAS score reduction between groups to show a clinical benefit [6,9]. We define significant pain relief as an absolute decrease in the mean VAS score of 25 mm.

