Thirty-two patients will be needed in each group to find a 25-mm difference between the group means on the VAS at 60 min, with a power of 0.80 and an alpha of 0.05. We will aim for 35 patients per group to account for about a 10% dropout rate. The groups will be compared using a *t*-test on gender, race, and age; and a chi (with Yates correction)-squared test on severity of presenting headache, to determine if they are similar. The individual VAS measurements will be compared using a repeated measures analysis of variance (ANOVA) test.

References:

- [3] Cicek M, Karcioğlu O, Parlak I, et al. Prospective, randomised, double blind,

controlled comparison of metoclopramide and pethidine in the emergency treatment of acute primary vascular and tension type headache episodes. *Emerg Med J.* 2004;21:323-326.

[7] Jones J, et al. Randomized double-blind trial of intravenous prochlorperazine for the treatment of acute headache. *JAMA.* 1989;261:1174-1176.

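### Baseline VAS is collected but given no role in the primary analysis, and the planned repeated measures ANOVA is not tied to the 60-minute difference that defines the primary outcome

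*Combined protocol and SAP*

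**What the plan says.** Under Methods of Measurement, each patient gives a baseline headache score on a 100-mm VAS, and then: "Repeat headache severity scores will be measured at 15, 30, 45, and 60 minutes".

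Under Outcome Measures, the primary outcome is the difference in pain scores between the arms, "measured as the absolute difference between the means at 60 min". No change score or baseline term is mentioned. One secondary outcome is "the difference between the rates of decline in pain scores", which may draw on baseline but does not adjust the primary comparison.

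Under Data Analysis:

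- The 25-mm benchmark is introduced by reference to earlier studies of between-group differences in VAS reduction. The plan then states: "We define significant pain relief as an absolute decrease in the mean VAS score of 25 mm".
- The sample size, 32 per group, is for "a 25-mm difference between the group means on the VAS at 60 min, with a power of 0.80 and an alpha of 0.05".
- Baseline severity has one stated use, a chi-squared "test on severity of presenting headache, to determine if they are similar". No consequence is attached to the result.
- The VAS analysis is a single sentence: "The individual VAS measurements will be compared using a repeated measures analysis of variance (ANOVA) test".

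**The concern.** Two things are missing.

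First, the analysis that decides the trial is not identified. The primary outcome is a contrast at one time, whereas a repeated measures ANOVA produces a group effect averaged over times, a time effect and an interaction. The plan does not say which of these answers the primary question, how the 60-minute difference is extracted, or whether baseline is a time point, a covariate or left out. The 25-mm sentence adds a third possibility, because it is worded as a decrease in a mean, while the outcome and sample size use a difference between groups. A raw 60-minute comparison, a change score and an averaged ANOVA effect are all defensible readings, and they do not have the same power.

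Second, a prognostic measurement already in hand goes unused. In a trial of about 32 evaluable patients per arm, chance differences in baseline pain can be appreciable. Testing whether the arms look alike neither corrects such a difference nor recovers precision; a covariate does both.

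**Working it through.** **Inputs.** From Data Analysis: 32 per arm, 25 mm, power 0.80, alpha 0.05. Not given in the documents, so assumed: two-sided testing, the SD, the baseline-to-60-minute correlation r, and the correlation between repeated scores.

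**1. The plan's own figure.** The 32 cannot be derived, because no SD is stated. Solving the two-sample t-test power equation (noncentral t, 62 df) for 80% power gives SD = 35.14 mm, used here as 35.1. Check:

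- SE = 35.1 × √(2/32) = 8.775 mm
- noncentrality = 25 / 8.775 = 2.85, giving power 0.801
- 95% CI half-width = 1.999 × 8.775 = 17.5 mm

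So 32 per arm fits an unadjusted 60-minute comparison with an SD near 35 mm. If alpha were one-sided, the implied SD would be about 39.8 mm.

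**2. Adding baseline as a covariate.** Residual SD = 35.1 × √(1 − r²), with 61 df. Estimating the slope multiplies the variance of the arm difference by 1 + 1/60 on average.

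| r | Residual SD (mm) | Power, slope cost ignored | Power, slope cost included | CI half-width, slope cost ignored (mm) |
|---|---|---|---|---|
| 0 | 35.1 | 0.80 | 0.794 | 17.5 |
| 0.1 | 34.9 | 0.805 | 0.798 | 17.5 |
| 0.3 | 33.5 | 0.836 | 0.830 | 16.7 |
| 0.5 | 30.4 | 0.899 | 0.894 | 15.2 |
| 0.6 | 28.1 | 0.939 | 0.935 | 14.0 |

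Break-even is where (1 − r²)(61/60) = 1, so r = √(1/61) = 0.13. A simulation of 8,000 trials per cell gave ANCOVA power of 0.794, 0.797, 0.833, 0.892 and 0.937 at these five values of r, against 0.799 to 0.804 unadjusted. Type I error was 0.045 to 0.050 for both analyses.

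**3. Chance baseline imbalance.** The part of the raw 60-minute difference carried over from baseline has a 95% range of ±1.96 × r × 35.1 × √(2/32): ±1.7, 5.2, 8.6 and 10.3 mm at r = 0.1, 0.3, 0.5 and 0.6. This is the same loss as the wider interval in step 2, not a further one: at r = 0.5, √(15.2² + 8.6²) = 17.5 mm.

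**4. If the ANOVA group effect decides the trial.** Assume SD 35.1 mm at every time and correlation 0.5 between any two scores. A patient's mean over k times then has SD 35.1 × √((1 + 0.5(k − 1))/k), and the arm difference has SE equal to that SD × √(2/32).

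| Times averaged | SD of mean (mm) | SE (mm) | Effect pattern | Average effect (mm) | Power |
|---|---|---|---|---|---|
| 15–60 min (k = 4) | 27.75 | 6.94 | 25 mm throughout | 25 | 0.94 |
| 15–60 min (k = 4) | 27.75 | 6.94 | 6.25, 12.5, 18.75, 25 mm | 15.6 | 0.60 |
| Baseline to 60 min (k = 5) | 27.19 | 6.80 | 0, then 25 mm throughout | 20 | 0.83 |
| Baseline to 60 min (k = 5) | 27.19 | 6.80 | 0, then 6.25 to 25 mm | 12.5 | 0.44 |

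In every row the true 60-minute difference is the 25 mm the trial was sized for.

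**5. If a change score decides the trial.** With equal SDs at both times, its SD is 35.1 × √(2(1 − r)). Power at 32 per arm is 0.60 at r = 0.2, 0.66 at r = 0.3 and 0.80 at r = 0.5.

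**The case against.** The strongest reply is that nothing here is an error. Omitting a covariate contradicts nothing in the documents, and a randomised comparison of 60-minute means is unbiased with correct type I error. That stands, and no bias is claimed.

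The size of the gain also depends on an unknown r. The Safety section permits any medication after 30 minutes, which could lower r; the absence of a minimum severity at entry could raise it. Below r of about 0.13 there is no gain, and the clear gains need r near 0.5, a value the documents do not support. This also stands, and is why a range is shown.

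A further reply is that step 2 compares ANCOVA with a t-test that the plan does not name for VAS. True, but the sample size is built on that contrast, and the absence of a named test for it is the specification gap itself.

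The scores entering the ANOVA may include baseline. The text does not say so, and entering baseline as one more time point is not the same as adjusting for it. As step 4 shows, it can reduce the power of the group effect.

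Finally, the sentence before the 25-mm definition refers to a difference between groups, and under randomisation the expected difference in reduction equals the expected difference in 60-minute means. The mismatch there is loose wording and a minor part of the point.

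**Conclusion.** The concern holds, as a change that should be made rather than a flaw that invalidates the trial. The plan states no role for baseline VAS in the primary analysis and does not connect its only VAS test to the primary contrast. Both statements follow from the text alone and need no assumption.

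The size does rest on assumptions. With two-sided alpha and the implied SD of 35.1 mm, covariate adjustment is worth about 0.03 of power at r = 0.3 and 0.09 at r = 0.5, with a cost below 0.01 if r is 0. The open choice of analysis has the larger effect: a trial sized for 80% power could be decided by a test with power anywhere from 0.44 to 0.94, under the equal-variance, correlation-0.5 illustration. Confidence is high in the omission, and lower in the amount of precision to be gained.

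**What to change.** Amend three sentences.

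- **Primary outcome (Outcome Measures).** Name one primary analysis: the arm difference in 60-minute VAS, with its 95% confidence interval, from an ANCOVA with baseline VAS as covariate. Alternatively, use the prespecified 60-minute arm contrast from a mixed model of the post-dose scores, with the same covariate.
- **ANOVA sentence (Data Analysis).** Replace it with that model, or keep it and label it, with any other VAS analysis, as secondary. State how baseline enters.
- **25-mm sentence (Data Analysis).** Reword it so that the benchmark applies to the adjusted between-group difference at 60 minutes.

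The sample size can stay as it is. The cost is one degree of freedom and no new data, since baseline VAS is already collected. The change should be fixed before any unblinded outcome data are seen.

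### The primary 60-minute VAS comparison takes no account of the baseline VAS already collected; the test is valid, but precision and protection against chance imbalance are given up at no saving

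*Combined protocol and SAP*

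**What the plan says.** The combined protocol and SAP touches this point in three places.

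- **Outcome Measures.** The primary outcome is the difference in pain scores between arms, "measured as the absolute difference between the means at 60 min". The speed at which pain falls is a secondary outcome.
- **Methods of Measurement.** Each enrolled patient gives a baseline headache severity on a 100-mm VAS. After dosing, "Repeat headache severity scores will be measured at 15, 30, 45, and 60 minutes".
- **Data Analysis.** For 80% power at a 5% significance level, the sample size rests on the same raw quantity as the primary outcome: "Thirty-two patients will be needed in each group to find a 25-mm difference between the group means on the VAS at 60 min". The target is supported by earlier studies that used a "25-mm difference in mean VAS score reduction between groups to show a clinical benefit", and significant relief is defined as a 25-mm fall in mean VAS. The arms are to be compared by a Yates-corrected chi-squared test on "severity of presenting headache, to determine if they are similar". The VAS measurements are then to be compared by repeated measures ANOVA. The plan does not say whether baseline is one of those measurements, or which term of the model tests the primary outcome.

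No baseline covariate, change-from-baseline primary endpoint or stratification by presenting severity is specified. The inclusion and exclusion criteria set no lower or upper limit on VAS at entry.

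**The concern.** Presenting pain is likely to predict pain an hour later, and with no entry limit on VAS it may vary widely between patients. In a raw comparison of 60-minute means that variation stays in the error term. If one arm happens to start with worse pain, part of the difference carries through to the primary estimate, in proportion to the slope of 60-minute VAS on baseline VAS.

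The similarity test does not help. It may flag an imbalance but does not remove it, and the plan does not say what follows if the arms differ. Adding adjustment only after seeing the baseline data would be a data-driven choice.

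What is at stake is the precision of the primary estimate, and how far a single small trial's result can be moved towards either drug by chance at entry, when the value needed to limit this is already on the data form.

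**Working it through.** **Inputs from the plan.** 32 per arm, 25-mm difference at 60 minutes, power 0.80, alpha 0.05 (sidedness not stated; two-sided assumed).

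**Inputs not in the plan.** The SD of 60-minute VAS is back-solved. The baseline to 60-minute correlation *r* is assumed to lie between 0.2 and 0.6. The baseline SD is assumed to be 15 to 25 mm, and is used only to describe the size of an imbalance and the slope.

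**Step 1: the plan's own figure.** Without an SD, 32 per arm cannot be reproduced directly. Solving the two-sample *t*-test for the SD that gives power 0.80 yields 35.1 mm (35.7 mm by the normal approximation). A one-sided test would imply 39.8 mm, which would scale the shifts in step 3 up by 39.8/35.1 = 1.13.

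**Step 2: chance baseline imbalance.** The SE of the difference in baseline means is baseline SD × √(2/32) = 0.25 × baseline SD. The expected absolute difference is 0.80 × SE and the 95% limit is 1.96 × SE.

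- Baseline SD 15 mm: SE 3.75, typical 3.0 mm, 95% limit 7.4 mm.
- Baseline SD 20 mm: SE 5.0, typical 4.0 mm, 95% limit 9.8 mm.
- Baseline SD 25 mm: SE 6.25, typical 5.0 mm, 95% limit 12.3 mm.

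**Step 3: carry-over to 60 minutes.** Shift = slope × imbalance, with slope = *r* × 35.1 / baseline SD. The baseline SD cancels, so the shift has SD *r* × 35.1 × 0.25 = *r* × 8.78 mm. Its typical (expected absolute) size is 0.80 × *r* × 8.78, and its 95% limit is 1.96 × *r* × 8.78.

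**Step 4: gain from adjustment.** The residual SD is 35.1 × √(1 − *r*²), and the confidence interval narrows by 1 − √(1 − *r*²). Power is from the same *t*-test at 32 per arm.

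| *r* | Typical shift (mm) | 95% limit (mm) | Residual SD (mm) | CI narrower by | Power |
|---|---|---|---|---|---|
| 0 (no adjustment) | – | – | 35.1 | – | 0.80 |
| 0.2 | 1.4 | 3.4 | 34.4 | 2% | 0.82 |
| 0.3 | 2.1 | 5.2 | 33.5 | 5% | 0.84 |
| 0.5 | 3.5 | 8.6 | 30.4 | 13% | 0.90 |
| 0.6 | 4.2 | 10.3 | 28.1 | 20% | 0.94 |

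Against the 25-mm target, the typical shift is 1.4/25 = 6% to 4.2/25 = 17%, and the 95% limit is 3.4/25 = 14% to 10.3/25 = 41%.

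**Step 5: are the assumed ranges coherent?** At *r* = 0.6 the slope is 0.6 × 35.1/15 = 1.40 for a baseline SD of 15 mm, 1.05 for 20 mm and 0.84 for 25 mm. A slope above 1 means that an imbalance grows by 60 minutes, which is hard to credit. The top row of the range is therefore plausible only if baseline scores are widely spread, near an SD of 25 mm.

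**Step 6: a plain change score instead.** With equal SDs at the two times, its SD is 35.1 × √(2(1 − *r*)). At *r* = 0.3 this is 41.5 mm, larger than the raw 35.1 mm, and power falls to about 0.66. It equals the raw comparison only at *r* = 0.5.

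**The case against.** The strongest reply is that nothing here is an error. Randomisation makes the raw 60-minute difference unbiased with overall type I error 0.05. Variation in presenting pain is already inside the implied SD of about 35 mm, and the trial is sized on the same raw quantity as its endpoint, so the nominal 80% power is not lost. All of that stands. A reader might infer that the primary result would be biased or invalid; the documents do not support that.

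Other strong readings also fail:

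- A reader might infer that imbalance passes one for one into the result. It carries over according to the slope, which the documents do not give.
- A reader might infer that large imbalances are to be expected. The 3 to 10 mm shifts are 95% limits; the typical size is 1 to 4 mm.
- A reader might see a defect in borrowing 25 mm from studies of VAS reduction. Under randomisation the expected difference in reductions equals the expected difference in 60-minute means, so the target transfers.

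Two further objections stand in part. Providers may give any further medication after 30 minutes (Safety section), which could weaken the correlation; this is why the range starts at 0.2, where the gain is small. And if baseline is among the repeated measurements, a group-by-time term would take starting level into account. But the plan does not say that it is, and that term tests something other than the stated 60-minute difference, while the group main effect would average baseline in. The sentence leaves the role of baseline open; it does not supply an adjusted 60-minute contrast.

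**Conclusion.** The point holds as a recommendation on precision, not as a finding of invalidity. The text is clear that the primary effect is the raw 60-minute difference and that no baseline covariate is named. The size is less certain, because it rests on a two-sided test, a back-solved SD of about 35 mm and an assumed correlation of 0.2 to 0.6. On those assumptions, adjustment is worth between 2 and 14 percentage points of power, and removes a chance shift that is usually a few millimetres and seldom beyond about 10. At the low end the benefit is slight; at *r* = 0.6 it equals having 32/(1 − 0.36) = 50 unadjusted patients per arm. Since the data are already collected, even the low end justifies the change.

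**What to change.** Keep VAS at 60 minutes as the primary outcome. In Outcome Measures and Data Analysis, prespecify the primary effect as the between-arm difference at 60 minutes adjusted for baseline VAS, either by ANCOVA or as the 60-minute contrast of a repeated-measures mixed model with baseline VAS as a covariate. Name which of the two is primary, and report the raw 60-minute means alongside.

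Do not substitute a plain change score, and do not let adjustment depend on the outcome of the baseline similarity test. A descriptive baseline table can still be shown.

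The cost is about one sentence in each section. No new data, patients or procedures are needed, and the sample size can stay as planned.

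### The plan's 25-mm definition of pain relief names no comparator, and the planned analysis names no baseline-adjusted 60-minute contrast to estimate the primary outcome

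*Combined protocol and SAP*

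**What the plan says.** All the relevant text is in the combined protocol and SAP, under Methods of Measurement, Outcome Measures and Data Analysis.

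- **Primary outcome (Outcome Measures).** Pain in the two arms is compared at a single time, "measured as the absolute difference between the means at 60 min". No threshold is attached.
- **Origin of the 25 mm (Data Analysis).** Earlier trials are said to have used a "25-mm difference in mean VAS score reduction between groups to show a clinical benefit".
- **Definition for this trial (Data Analysis, next sentence).** "We define significant pain relief as an absolute decrease in the mean VAS score of 25 mm".
- **Sample size (Data Analysis).** The size of 32 per arm is chosen "to find a 25-mm difference between the group means on the VAS at 60 min". Power is set at 0.80 and alpha at 0.05. No SD is given, and the test is not said to be one- or two-sided.
- **Analysis of VAS (Data Analysis).** The VAS measurements are to be compared by repeated measures ANOVA. No contrast, time point or covariate is named.
- **Data available (Methods of Measurement).** VAS is recorded at baseline and at 15, 30, 45 and 60 minutes.

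**The concern.** The one sentence in which the plan defines a meaningful effect in its own voice describes a fall in a mean. The trial is designed to estimate something else, a difference between two means. A fall in one arm can come from natural improvement, regression to the mean, or other medication, which the Safety section permits after 30 minutes and so before the 60-minute score. The Selection of Participants section itself says that undifferentiated headaches improve with all the usual drugs, so a sizeable fall in the control arm is to be expected.

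The analysis section does not resolve this. A repeated measures ANOVA with arm and time produces an arm effect averaged over time points and an arm-by-time interaction. Neither is the 60-minute difference. Unless a contrast is specified, the primary outcome has no planned estimate or confidence interval to set beside the 25 mm. The plan will compare presenting severity between arms but does not say that the treatment comparison is adjusted for it, nor whether baseline enters the ANOVA as one of the repeated scores. Precision that costs nothing to obtain may be lost, and the choice of estimate is left open until the data are seen.

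**Working it through.** **1. The wordings side by side**

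| Place | Quantity | Compares arms? | Time named? |
|---|---|---|---|
| Primary outcome | difference between means | yes | 60 min |
| Sample size | 25-mm difference between means | yes | 60 min |
| Definition of pain relief | 25-mm decrease in the mean | none named | none |

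The primary outcome and the powered effect agree. Only the definition differs. For illustration, if both arms start equal and both fall 30 mm, each meets the literal definition, the difference between arms is 30 − 30 = 0, and a two-sided test rejects at its alpha of 0.05.

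**2. The plan's own figure**

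Inputs from the Data Analysis section: difference 25 mm, power 0.80, alpha 0.05, 32 per arm. The SD is missing, so 32 cannot be reproduced directly and the SD is solved for instead. A two-sided test and equal arms are assumed.

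- Normal approximation: n = 2·SD²·(1.960 + 0.842)²/25². At SD 35, this is 2 × 1225 × 7.85/625 = 30.8, so 31.
- Two-sample t-test (noncentral t): at SD 35, n = 32. The SDs that give exactly 32 are about 34.6 to 35.1 mm.
- A one-sided t-test would imply an SD of about 39.2 to 39.8 mm.

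The figure of 32 is attainable and is not shown to be wrong. The steps below take SD 35 mm, two-sided.

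**3. Precision of the unadjusted 60-minute difference**

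SE = SD·√(2/n) = 35 × √(2/32) = 35 × 0.25 = 8.75 mm. The 95% CI half-width is 2.00 × 8.75 = 17.5 mm (t with 62 degrees of freedom).

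If the true difference is exactly 25 mm, the estimate falls below 25 half the time, and the CI lies wholly above 25 only about 2.5% of the time. The trial is powered to distinguish 25 mm from zero. It is not powered to show an effect greater than 25 mm.

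**4. Effect of adjusting for baseline VAS**

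With correlation ρ between baseline and 60-minute VAS, the residual SD in an ANCOVA is SD·√(1 − ρ²). The documents give no ρ, so a range is shown. Power is for a 25-mm difference with 32 per arm.

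| Assumed ρ | Residual SD (mm) | SE = residual SD × 0.25 (mm) | Power |
|---|---|---|---|
| 0 (no gain) | 35.0 | 8.75 | 0.80 |
| 0.2 | 34.3 | 8.57 | 0.82 |
| 0.3 | 33.4 | 8.35 | 0.84 |
| 0.41 | 31.9 | 7.98 | 0.87 |
| 0.5 | 30.3 | 7.58 | 0.90 |

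The gain is small at low correlation and worthwhile from about 0.3 upward. The loss of one degree of freedom for the covariate does not change these figures to two decimals.

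**The case against.** The strongest reply is that the sentence is loose shorthand. It stands between a statement about a difference between groups and a sample size for a difference between group means, so a sympathetic reader would carry the comparison across. That reading is plausible and cannot be excluded, but the text does not state it.

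Three stronger readings are tempting, and the documents do not support them.

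- *A reader might infer that the plan adopts three rival definitions of 25 mm.* The difference in reductions is attributed to earlier trials as the source of the number. The trial's own uses are two. Under randomization, moreover, the difference in reductions and the difference in 60-minute means have the same expected value. They differ in a given sample by the chance baseline gap. With an assumed baseline SD of 20 mm, that gap has SE 20 × 0.25 = 5.0 mm, a median size of 0.674 × 5.0 = 3.4 mm, and a 95% bound of 1.96 × 5.0 = 9.8 mm. This is sampling noise, not a second treatment effect.
- *A reader might infer that the success criterion contradicts the primary outcome.* No section makes 25 mm a success rule. The defined term is not used again in any outcome, test or responder rate, and the powered effect matches the primary outcome. That a within-arm fall would be reported as efficacy of ketamine is speculation.
- *A reader might infer that the sample size is wrong.* An SD near 35 mm yields 32, so nothing shows an error.

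It is also fair to say that baseline adjustment is a separate matter from the wording, and that its benefit depends on an unknown correlation. Both points stand. They limit the size of the claim. They do not remove the need for a named 60-minute estimate.

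Finally, medication given after 30 minutes also affects the between-arm comparison at 60 minutes, so rewording the definition does not settle that issue.

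**Conclusion.** The point holds in a limited form. The definition of pain relief lacks a comparator and a time, and no other passage reconciles it with the between-arm, 60-minute quantity that the trial measures and is powered for. Alone, that is a minor clarification. The more useful part is the analysis: the repeated measures ANOVA names no 60-minute contrast and does not say that baseline VAS is adjusted for, so the primary outcome lacks a specified estimate. Supplying a baseline-adjusted one would raise power from 0.80 to about 0.82, 0.84, 0.87 and 0.90 at correlations of 0.2, 0.3, 0.41 and 0.5.

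These figures assume 32 per arm, a two-sided test, an SD of about 35 mm inferred from the sample size, and the stated correlations. The primary comparison and the sample size are not shown to be in error. The change should be made, but the trial does not depend on it.

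**What to change.** 1. Replace the definition with a statement that 25 mm is the difference between arms in mean VAS at 60 minutes used for the sample size. Add the SD assumed and whether the test is two-sided.
2. Name the primary analysis: ANCOVA of 60-minute VAS on arm with baseline VAS as covariate, or the 60-minute contrast of a mixed model with the same covariate. Report the estimated difference and its 95% CI. The repeated scores can still be used for the secondary question of rate of decline.
3. Use 25 mm to discuss clinical relevance. Do not require the CI to exceed it, because an unadjusted half-width of about 17.5 mm makes that unattainable for effects near 25 mm.
4. Label falls within each arm as descriptive.

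The cost is a few sentences and one covariate that is already collected, with no extra patients or visits. The change does replace the analysis now written, so it should be fixed before unblinding. The plan should also say how a missing baseline score is handled and, if a mixed model is chosen, which covariance structure is used.

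### The baseline comparison names a t-test for gender and race and a Yates chi-squared test for headache severity, which is recorded only on a continuous 100-mm VAS (minor)

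*Combined protocol and SAP*

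**What the plan says.** The Data Analysis section gives one sentence to baseline comparability. It names a t-test and a chi-squared test, allocated as "test on gender, race, and age; and a chi (with Yates correction)-squared test on severity of presenting headache", and states the purpose as "to determine if they are similar".

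Methods of Measurement lists what the enrolment form records: "age, sex, race, phone number, and baseline headache severity using a 100-mm visual analog scale (VAS"). It gives no coding or number of categories for race, and no severity categories.

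Elsewhere the VAS is treated as continuous. Under Outcome Measures the primary outcome is "measured as the absolute difference between the means at 60 min", and Data Analysis adds "The individual VAS measurements will be compared using a repeated measures analysis of variance (ANOVA) test". The 25-mm figure in Data Analysis is a change or a between-group difference, not a baseline category. The enrolment target is stated as "We will aim for 35 patients per group to account for about a 10% dropout rate".

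**The concern.** Of the four baseline variables, only age is paired with a conventional test. A t-test compares means, and a nominal variable such as race has no meaningful mean once it has more than two categories. A Yates-corrected chi-squared test needs a 2x2 table, so the VAS would have to be cut in two at a point the plan does not state. The likely intention was the reverse: chi-squared for the categorical items and a t-test for severity. Nothing in the document confirms or repairs this.

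What is at stake is the trial's statement that the arms were alike at baseline. The race result could turn on category numbering. Severity, which is measured on the same scale as the primary outcome, would get the less sensitive test. Both the cut-point and the race coding would remain open until data are in hand.

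A separate weakness would survive a simple swap of the tests: a non-significant result at 35 per arm does not show that the arms are similar.

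**Working it through.** The plan gives no figure for this point to reproduce. From the document come 35 per arm, the 100-mm VAS and the named tests. The race tables, the median split, the baseline mean and the SDs are assumptions.

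**Gender, or race with two categories.** With 35 per arm there are 36 x 36 = 1,296 possible tables, of which 4 have no variation in either arm. In the other 1,292 the t-test on 0/1 codes and the Pearson chi-squared test give the same verdict at 0.05 every time.

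**Race, four categories.** Illustrative counts are 14/8/9/4 v 8/16/7/4.

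- Chi-squared: expected counts are 11, 12, 8 and 4 in each arm, so X² = 2 x (9/11 + 16/12 + 1/8 + 0) = 4.55 on 3 df, p = 0.21.
- t-test, categories numbered 1, 4, 2, 3: means 76/35 = 2.17 v 98/35 = 2.80, p = 0.036.
- t-test, categories numbered 1, 2, 4, 3: means 78/35 = 2.23 v 80/35 = 2.29, p = 0.84.
- Of 24 numberings, 2 fall below 0.05. Reversing the numbers leaves p unchanged, so this is 1 of 12 distinct numberings.

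**Race, three categories.** Merging the last two gives 14/8/13 v 8/16/11. The t-test p runs from 0.039 to 0.56 over 6 numberings (2 below 0.05, or 1 of 3 distinct). Chi-squared gives X² = 2 x (9/11 + 16/12 + 1/12) = 4.47 on 2 df, p = 0.11.

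**Race, no true difference.** In 20,000 simulated trials for each of four assumed race mixes, the verdict at 0.05 differed between numberings in 22-24% of trials with four categories and in about 12% with three. This measures dependence on numbering. It is not a false-positive rate.

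**Severity, Yates test on an assumed median split.** The statistic is n(|ad - bc| - n/2)² / (product of the four margins), with n = 70 and every margin 35.

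- 22/13 v 13/22 (63% v 37% above the median): 70 x (315 - 35)² / 35⁴ = 3.66, p = 0.056.
- 23/12 v 12/23: 70 x (385 - 35)² / 35⁴ = 5.71, p = 0.017.
- The test therefore rejects only from 23/12 outwards. Its exact (hypergeometric) rejection rate with no difference is 1.6%, against a nominal 5%.

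**Severity, chance of flagging a 10-mm imbalance.** Simulation used 200,000 trials per setting, 35 per arm, and normal values with nominal mean 65 mm in the first arm. Each cell is Yates v t-test.

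| Setting | SD 20 mm | SD 25 mm | SD 35 mm |
|---|---|---|---|
| Nominal 65 v 75, bounded to 0-100 (realised gap 9.3/8.8/7.8 mm) | 23% v 54% | 14% v 37% | 7% v 21% |
| Bounded, realised gap 10 mm, second arm higher | 27% v 59% | 19% v 46% | 12% v 31% |
| Bounded, realised gap 10 mm, second arm lower | 24% v 56% | 16% v 42% | 10% v 28% |

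The document gives no baseline SD. The 35 mm comes from the sample-size statement, "Thirty-two patients will be needed in each group to find a 25-mm difference between the group means on the VAS at 60 min". Taking the 80% power and 5% alpha given there, and assuming a two-sided test, 25 x √(32/2) / (1.960 + 0.842) = 35.7 mm by the normal approximation, or 35.1 mm by the t-test. It is an implied 60-minute SD, used here only as an upper value.

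**What a non-significant t-test allows.** The largest observed gap that stays non-significant is t(0.975, 68) x SD x √(2/35) = 1.995 x SD x 0.239. This is 9.5, 11.9 and 16.7 mm at observed SDs of 20, 25 and 35 mm.

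**The case against.** The strongest reply is that little follows from the mismatch. Gender is not a working error, as the exhaustive check shows. The race problem exists only with more than two categories, which the document does not establish. Any one numbering fixed in advance keeps a false-positive rate of about 5%, so numbering matters for error rates only if it is chosen after seeing the data, and nothing suggests that. Mirror-image numberings also double the raw counts. The severity percentages rest on an assumed split, mean and SDs. At a nominal 35 mm, bounding brings the realised SDs down to about 29 and 27 mm and puts about 16% and 24% of patients at exactly 100. The objection to testing for similarity applies to any baseline test, including correctly assigned ones.

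All of this is fair, and it limits the size of the point. It does not remove it. Even with a fixed numbering, a t-test on a nominal variable with more than two categories answers a question set by that numbering. The fractions (1 in 12, 1 in 3) are the same once mirror images are dropped. The loss of sensitivity from cutting the VAS appears in every setting tried. The severity test still has no cut-point, and no other text supplies one.

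**Conclusion.** The concern holds, as a minor error in the written plan. The severity test cannot be run without an unstated cut-point, and the race test is unsuitable if race has more than two categories. Gender is unconventional but harmless, and age is correctly placed. That the tests were transposed is an inference.

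Under the assumed median split, the Yates test would flag a 10-mm severity imbalance less than half as often as a t-test in every setting examined. The exact percentages depend on the assumed mean and SDs; the direction does not. Neither test can establish similarity.

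The effect stops at the baseline statement. The 60-minute comparison, the repeated measures ANOVA, the sample size and alpha do not change, and under randomisation any baseline imbalance is due to chance.

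**What to change.** In Data Analysis, replace the baseline sentence with descriptive summaries by arm: counts and percentages for gender and race, mean and SD for age and baseline VAS. Do not use p-values to declare the arms similar. If tests are kept, use chi-squared or Fisher's exact test for gender and race (a Yates correction applies only to a 2x2 table), and a t-test or mean difference with 95% CI for age and baseline VAS.

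Optionally, and separately from the error itself, include baseline VAS as a covariate in the 60-minute comparison, which deals with chance imbalance directly. Relative to an unadjusted 60-minute comparison, the standard error falls by 1 - √(1 - r²): about 5%, 13% and 29% at assumed baseline-to-60-minute correlations of 0.3, 0.5 and 0.7. The gain over the planned repeated measures ANOVA may be smaller if that analysis already includes the baseline score.

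The cost is one sentence, plus one more if the covariate is added. No new data are needed, and sample size and alpha stay as they are.
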